- a) Nivolumab 480 mg using a 30-min i.v. infusion every 4 weeks (Q4W). Regorafenib starting dose 90 mg orally every day (QD) for 3 weeks of every 4 weeks (i.e. 21 days on, 7 days off). If starting the dose of 90 mg is well tolerated (absence of any grade rash/HFSR or other Grade 2 or higher clinically significant toxicity. Lab abnormalities of any grade that resolve to ≤G1 within 72 hours are acceptable) the dose can be escalated to 120 mg orally daily anytime after C1, starting with C2D1.
- b) Mandatory safety FU visit (30 d + 7 d after study treatment discontinuation and 100 d + 14 d after LD of nivolumab) and other active FU visits to collect safety and efficacy information for participants who discontinue study treatment without disease progression, if applicable

Figure 4–2 Study Schema

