4.1.2 Treatment Phase

The start of the treatment period is defined by the first administration of study treatment. The length of a cycle is 28 days (plus a potential time window, for acceptable deviation see Section 1.3 SoA). Participants will be treated with nivolumab intravenously given on Day 1 and regorafenib orally every day for 3 weeks of a 4 week cycle. Nivolumab will be administered as a flat dose of 480 mg using a 30 min i.v. infusion Q4W. Regorafenib will be given at a starting dose of 90 mg for 21 days of every 28-day cycle (i.e., 21 days on, 7 days off). If the starting dose of 90 mg daily is well tolerated (absence of any grade rash/hand foot skin reaction (HFSR) or other Grade 2 or higher clinically significant toxicity) the dose can be escalated to 120 mg orally daily anytime after Cycle 1, starting with Cycle 2 Day 1. The Sponsor will be immediately informed, if the Investigator decides not to escalate the dose to 120 mg on C2D1 despite meeting the criteria.

Dose modification guidelines for dose reduction in case of toxicity are detailed in Section 6.6. Treatment with individual drugs (regorafenib or nivolumab) may continue on schedule even if the other drug is interrupted or permanently discontinued due to toxicity.

Participants who complete 24 infusions of nivolumab (after approximately 2 years of treatment) need to discontinue treatment with nivolumab. Regorafenib monotherapy treatment can be continued beyond 2 years until discontinuation criteria are met.

During the study, participants will undergo evaluations for safety, efficacy, pharmacokinetics and tissue and blood for biomarker will be collected.

Response will be assessed by imaging and participants may continue treatment until confirmation of disease progression per response evaluation criteria in solid tumors for trials testing immunotherapeutics (iRECIST; Section 10.6.2) or per immune response assessment in neuro-oncology (iRANO; Section 10.6.4), unacceptable toxicity or any other protocol defined criterion for withdrawal occurs. See Section 8.1 for further details on treatment continuation and tumor assessments beyond progression per RECIST 1.1 or RANO criteria. Primary endpoint of the study for all cohorts is ORR as measured by RECIST 1.1 or RANO for GBM/AA as determined by the investigator. For GBM/AA tumor assessment per RANO will

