Regorafenib will be given orally every day for 3 weeks of each cycle. Each treatment cycle will be 28 d in duration. Regorafenib will be given as 30 mg tablets QD for 3 weeks of every 4 weeks (i.e., 3 weeks on, 1 week off) as a starting dose of 90 mg. If starting dose of 90 mg daily is well tolerated (absence of any grade rash/HFSR or other Grade 2 or higher clinically significant toxicity; lab abnormalities of any grade that resolve to \leq Grade 1 within 72 hours are acceptable) dose can be escalated to 120 mg orally daily anytime after Cycle 1 starting with C2D1. Sponsor should be informed immediately, if the Investigator decides to not escalate the dose to 120 mg despite meeting the criteria.

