6.1 Study Intervention(s) Administered

Table 6–1 Administration of Study Intervention

Study Intervention	Regorafenib	Nivolumab	
Туре	small molecule drug (MKI)	monoclonal antibody (mAB), biologic	
Dose Formulation	tablet	solution for infusion	
Unit Dose Strengths	30 mg / tablet	100 mg / 10 mL vial (10 mg/mL)	
Dosage Levels	3x 30 mg tablets every day (q.d.) for 21 days of every 28-day cycle (21 days on, 7 days off) as a starting dose of 90 mg. If the starting dose is well tolerated dose should be escalated to 120 mg (4x30 mg tablets) starting with C2D1.	480 mg (5x100 mg / 10 mL vials) on D1 of each cycle	
Route of Administration	oral	i.v. infusion	
Use	experimental	experimental	
IMP and NIMP	IMP	IMP	
Sourcing	Regorafenib will be provided centrally by the Sponsor.	Nivolumab will be provided centrally by the Sponsor.	
Packaging and Labeling	Regorafenib is available in high density polyethylene bottles with a white child resistant closure and induction seal. The packaging configuration is 21 tablets Regorafenib 30 mg and a 3 g desiccant per bottle. The bottles will be labeled as required per country requirement.	Nivolumab will be provided in glass injection vial. Each glass injection vial will be labeled as required per country requirement.	
Current/Former Name(s) or Alias (es)	Stivarga / BAY 73-4506	Opdivo®	

Abbreviations: IMP = Investigational medicinal product; i.v. = Intravenous; mAB = Monoclonal antibody; MKI = Multikinase inhibitor; NIMP = Non-investigational medicinal product

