6.6 Dose Modification

Based on the known toxicity profiles of regorafenib and nivolumab, certain AEs are likely to be associated with one drug versus the other. For example, treatment emergent hypertension and HFSR are likely to be associated with regorafenib rather than nivolumab; similarly, immune-related AEs are likely to be associated with nivolumab rather than regorafenib. However, some drug-related AEs such as diarrhea, abnormal thyroid function, and fatigue are overlapping. Therefore, it is important to evaluate each AE to confirm etiology or exclude other causes in order to determine proper management of the adverse reaction and action regarding study treatment. A careful decision should be made by Investigators based on all clinical information, e.g., relatedness to study medications.

Dose modifications must be based on the maximum toxicity experienced during a cycle. The length of a cycle is 28 days (plus a potential time window, for acceptable deviation see Section 1.3 SoA). If appropriate, the Investigator may attribute each toxicity event to regorafenib or nivolumab alone or to the combination. In situations where clear attribution cannot be made to individual drugs, more conservative dose modification approach should be used for both drugs. In case of dose modifications, any efforts should be made to restart study intervention as per original schedules for regorafenib and nivolumab.

The dose modification can occur independently for the 2 drugs used if toxicity can be clearly attributed to one of the drugs. Resumption of regorafenib dosing is not dependent on resumption of nivolumab and vice versa. Treatment with individual drugs (regorafenib or nivolumab) may continue on schedule even if other drug is interrupted or permanently discontinued due to toxicity.

A cycle will be defined as 28 days regardless of interruptions.

- In case of interruption regorafenib is allowed to be re-started during the cycle within day 1 and day 21, regorafenib should not be restarted in the off week. Missed doses of regorafenib will not be replaced in the off week.
- For nivolumab dosing occurs on day 1 of every cycle
- Per protocol dose reduction or increase of nivolumab is not allowed

6.6.1 Toxicity Management, Dose Modification and Permanent Discontinuation Recommendations for Regorafenib

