Table 6–2 outlines different regorafenib dose levels for the purpose of dose modification. In case a dose reduction for regorafenib is necessary, the study intervention will be administered as outlined in Table 6–2 to Table 6–6.

	days on, 7 days off)	Daily Regorafenib (21 days on, 7 days off from cycle 2 onwards if escalation if feasible)
Dose Level 0	90 mg	120 mg
Dose Level -1	60 mg	90 mg
Dose Level -2	NA	60 mg ^a

Table 6–2 Dose Levels for Regorafenib

Abbreviations: NA = Not applicable

a) If reductions are required resulting in regorafenib daily dose of less than 60 mg, then regorafenib will be permanently discontinued.

Table 6–3	Dose Modification/Dose Interruption Guide for Regorafenib-Related
Toxicities	

CTCAE Grade	Occurrences	Dose Interruption	Dose modification (when resuming treatment)
Grade 0-2 ^c	Any	No change	No change
Ore de Of	1 st and 2 nd occurrence	Hold until recovery to <g2 baselinea</g2>	Restart at same dose level or reduce 1 dose level (at the investigator's discretion)
Grade 3 ^c	3 rd occurrence	Hold until recovery to <g2 baselinea</g2>	Reduce 1 dose level or consider permanent discontinuation ^b
Grade 4 ^c	Any	-	Discontinue

Abbreviations: CTCAE = Common terminology criteria for adverse events; G = Grade; HFSR = Hand-foot skin reaction

a) Excludes alopecia, non-refractory nausea/vomiting, lymphopenia and asymptomatic laboratory abnormalities. Treatment can be resumed with Grade 2 fatigue or hypothyroidism.

- b) If reductions are required resulting in regorafenib daily dose of less than 60 mg, then regorafenib will be permanently discontinued. If toxicity returns to Grade 0-1 after dose reduction, dose reescalation is permitted in the subsequent cycle at the investigator's discretion. Participants requiring a delay of >4 weeks should discontinue regorafenib treatment. However, continuation of regorafenib may be considered if, in the investigator's opinion, the participant may continue to benefit from the regorafenib treatment, and after consultation with Sponsor.
- c) Discontinuation is required for severe bleeding necessitating urgent medical intervention, gastrointestinal perforation or fistula of any grade and posterior reversible encephalopathy syndrome (PRES) of any grade.

Page 54 of 135

Skin toxicity grade (CTCAE)	Occurrence	Dose Interruption	Dose modification (when resuming treatment)	

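### The 72-hour laboratory exception can permit 120 mg at C2D1 after a Cycle 1 liver-test rise for which Tables 6-6 and 6-2 direct 60 mg, and no sentence says which rule prevails

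*Protocol*

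**What the plan says.** **The escalation rule** appears in four places in the protocol.

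- Figure 4-1 footnote a (Section 4.1) lets the dose go from 90 to 120 mg from C2D1 if 90 mg is well tolerated. That means no rash or hand-foot skin reaction of any grade and no other clinically significant toxicity at Grade 2 or above. It then adds: "Lab abnormalities of any grade that resolve to ≤G1 within 72 hours are acceptable".
- The opening of Section 6 carries the same exception: "within 72 hours are acceptable) dose can be escalated to 120 mg orally daily anytime after Cycle 1".
- Section 4.1.2 gives the definition without the exception: "or other Grade 2 or higher clinically significant toxicity) the dose can be escalated to 120 mg orally daily anytime after Cycle 1". It also provides for declining: "The Sponsor will be immediately informed, if the Investigator decides not to escalate the dose to 120 mg on C2D1 despite meeting the criteria".
- Table 6-1 uses firmer wording and does not define the term: "If the starting dose is well tolerated dose should be escalated to 120 mg (4x30 mg tablets) starting with C2D1".

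**The reduction rule** is in Section 6.6.

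- The general principle is "Dose modifications must be based on the maximum toxicity experienced during a cycle".
- Section 6.6.1 adds: "In case a dose reduction for regorafenib is necessary, the study intervention will be administered as outlined in Table 6–2 to Table 6–6".
- Table 6-6 covers a first AST/ALT above 3 and up to 5 x ULN, or total bilirubin above 1.5 and up to 3 x ULN, from a normal baseline. Dosing is held until recovery and then resumes one level lower. Footnote b lets re-escalation be considered once values have been stable for two complete cycles.
- Table 6-2 puts one level below 90 mg at 60 mg.

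**The concern.** A transient liver-test rise can satisfy the escalation rule and trigger the liver table at the same time. One route leads up to 120 mg and the other down to 60 mg.

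The liver rule looks deliberately cautious. The footnotes to Tables 6-3, 6-4 and 6-5 allow re-escalation in the next cycle after recovery to Grade 0-1. Table 6-6 asks for two stable cycles and closer testing after any re-escalation. A 72-hour route to 120 mg runs against that.

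At stake is a participant receiving twice the dose the liver table calls for, shortly after a liver-test event. Section 2.3 names raised transaminases as common with regorafenib and transaminitis as a possible overlapping effect with nivolumab. With about 60 sites planned (Section 4.1), each would have to settle the question alone.

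**Working it through.** The plan gives no figure to reproduce. The check follows one participant through both rules and then looks at timing.

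**The case.** Normal baseline; first AST/ALT of, say, 4 x ULN in Cycle 1 on 90 mg, clearly attributed to regorafenib. It returns to Grade 1 or lower within 72 hours. There is no rash, hand-foot skin reaction or other relevant toxicity, and no AST/ALT above 3 x ULN together with bilirubin above 2 x ULN (Table 6-6 discontinues for that).

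**Dose at C2D1.**

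| Rule | Result |
|---|---|
| Figure 4-1 footnote a; Section 6 | 120 mg permitted |
| Table 6-1 | 120 mg, worded *should* |
| Section 4.1.2 (no 72-hour exception) | 120 mg permitted only if the event is not judged a clinically significant Grade 2 or higher toxicity |
| Table 6-6 with Table 6-2 | 60 mg |

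- Ratio: 120 / 60 = 2.
- Over Cycle 2, with 21 dosing days: 21 x 120 = 2,520 mg against 21 x 60 = 1,260 mg.
- Re-escalation under footnote b, if Cycles 2 and 3 are the stable cycles: 2 x 28 = 56 days after C2D1, so C4D1 at the earliest.

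**When the rules meet directly.** Section 6.6 limits restarts to the dosing weeks: "within day 1 and day 21, regorafenib should not be restarted in the off week". The last Cycle 1 dosing day is D21 and C2D1 is nominally D29. If recovery takes the full 72 hours, the Cycle 1 dosing days left for resumption are max(0, 21 - (event day + 3) + 1).

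| Visit with liver tests | Clears | Days left | With the ±2-day window |
|---|---|---|---|
| D8 | D11 | 21 - 11 + 1 = 11 | 13 to 9 |
| D15 | D18 | 21 - 18 + 1 = 4 | 6 to 2 |
| D22 | D25 | 0 | 0 |

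After a D8 or D15 event the participant would normally resume at 60 mg within Cycle 1, and no text describes a step from 60 to 120 mg. After a D22 event the resumption dose is first set at C2D1, the day the escalation rule first applies. D22 does have a limited chemistry panel, which includes AST, ALT and bilirubin (Section 1.3; Table 10-1).

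**Whether 72-hour recovery would be seen.** The next scheduled chemistry falls within 2 days before C2D1 (Section 1.3, footnote g), nominally D27 to D29. That is 5 x 24 = 120 to 7 x 24 = 168 hours after D22. Table 6-6 footnote a asks for liver tests at least weekly. At nominal timing, showing recovery within 72 hours therefore needs an extra test by D25. At the edge of the window, a D24 visit with a D27 test is exactly 72 hours.

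**The case against.** The best reply is that the protocol already leans towards the lower dose.

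- **Maximum toxicity.** Section 6.6 ties dose modification to the worst toxicity in the cycle. It treats a nivolumab increase as a kind of modification, and Table 6-2 includes the 120 mg column. The principle therefore arguably governs the escalation decision too.
- **Unclear attribution.** Sections 6.6 and 6.6.2 call for the more cautious option for both drugs when an event cannot clearly be assigned to one. Many transaminase rises on this combination would fall there. The concern is left only with events clearly attributed to regorafenib.
- **Permission against direction.** Three of the four escalation texts say *can*, so reducing the dose complies with both rules. Only Table 6-1, a dosing summary, says *should*. Declining to escalate leads only to a sponsor notice.
- **Status of the table.** Table 6-6 is titled a guide, in a section headed as recommendations, so it directs 60 mg rather than strictly requiring it. At D22 the drug is already off, so applying the resumption column to a planned cycle start is a reasonable interpretation rather than express text.
- **Safeguards.** Chemistry is repeated before C2D1 and at C2D8 and C2D15, and a recurrence in this row means discontinuation.

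All of this stands, and it narrows the point. It does not remove it. The maximum-toxicity sentence does not mention the 72-hour exception, whose purpose is to disregard a short-lived peak. Section 4.1.2 points to Section 6.6 for reductions without ranking the rules. That a specific table outranks a general rule is an inference, and the 72-hour sentence is itself specific to laboratory values at this decision.

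A reader might infer that the protocol obliges sites to double the dose, or that nothing in it favours the reduction. The documents support neither reading.

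**Conclusion.** The point holds in narrow form, as a minor participant-safety correction with moderate confidence. For the case traced above, the protocol can permit 120 mg at C2D1 while its liver table directs 60 mg, and no sentence expressly ranks them. Separately, well tolerated has two definitions, and Section 4.1.2 has the stricter one.

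The factor of 2 applies per affected participant. It assumes a normal baseline, a first event, clear attribution to regorafenib, no other relevant toxicity, documented 72-hour recovery, and in practice an event around D22. The documents give no frequency, so none is assumed; the number affected may be zero.

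A reader might extend the clash to every liver-test rise. Table 6-6 does not support that:

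- Values below 3 x ULN from a normal baseline, or above 3 and up to 5 x ULN from a raised baseline, need no change.
- AST/ALT above 5 x ULN or bilirubin above 3 x ULN makes restart a matter of judgement.
- The discontinuation rows leave no dose to escalate.

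Nor is there any effect on the objective response rate endpoint, the stage boundaries or the error rates.

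**What to change.** Use one definition of well tolerated in Figure 4-1 footnote a, Section 4.1.2, Section 6 and Table 6-1, and add a precedence statement:

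> Tables 6-3 to 6-6 take precedence over this escalation rule. The 72-hour exception covers only laboratory abnormalities that trigger no dose reduction or discontinuation under those tables. After a Table 6-6 reduction, escalation follows footnote b.

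The cost is a text change in four places and a letter to sites, with no change to sample size, endpoints or analyses. The downside is that slightly fewer participants would escalate at C2D1.

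SAP version 3.0 addresses the final analysis after all participants have left the trial. If dosing is over, what remains is to check whether anyone was escalated at C2D1 after an event in this Table 6-6 row, and to avoid reusing the wording.

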27 JAN 2021

Page 31 of 135

Abbreviations: AA = Anaplastic Astrocytoma; BTC = Biliary Tract Carcinoma; ChT = Chemotherapy; DCR = Disease control rate; DOR = Duration of response; ECOG PS = Eastern Cooperative Oncology Group Performance Status; ESCC = Esophageal Squamous Cell Carcinoma; GBM = Glioblastoma Multiforme; HNSCC = Head and Neck Squamous Cell Carcinoma; IO = Immune oncology; IV = Intravenous; ORR= Overall Response Rate; OS = Overall survival; PDAC= Pancreatic ductal adenocarcinoma; PFS = Progression free survival; PK = Pharmacokinetics; PO = Per oral; q4wk = Every 4 weeks; QD = Once daily; RECIST 1.1 = Response Evaluation Criteria In Solid Tumors 1.1; RANO = Response assessment in neuro-oncology; R/M = Recurrent/Metastatic

Each cohort starts with the Stage 1 and may continue to the Stage 2 if sufficient efficacy will be observed.

Stage 1 of the study:

Tumor based cohorts will recruit as follows:

- approximately 9 participants will be treated for the HNSCC (IO naïve), ESCC and GBM/AA (participants with AA are included only in Stage 2) cohorts
- approximately 14 participants will be treated for the HNSCC (IO treated) cohort
- approximately 17 participants will be treated for the PDAC and BTC cohorts

Stage 2 of the study:

Tumor based cohorts that pass the pre-defined ORR threshold of the Stage 1 may expand as follows:

- approximately 21 participants will be treated for the HNSCC (IO naïve), ESCC and GBM/AA cohorts
- approximately 6 participants will be treated for the HNSCC (IO treated) cohort
- approximately 28 participants will be treated for the PDAC and BTC cohorts

Information about the respective Cohort of the participant will be recorded by the investigator or delegate in IxRS after signing off the participant information/informed consent form (PI/ICF).

CONFIDENTIAL

Clinical Study Protocol Global Amendment 1 BAY 73-4506/ 21136

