To explore pharmacodynamic effects of regorafenib and nivolumab combination on e.g. immune environment, signaling pathway activity, and downstream processes	Change from baseline in levels of biomarkers in tumor, blood or stool samples	
 To further investigate the study intervention and similar drugs (i.e., mode-of-action-related effects and / or safety) and to further investigate pathomechanisms deemed relevant to cancer and associated health problems 	 Various biomarkers (e.g., diagnostic, safety, pharmacodynamic, monitoring, or potentially predictive biomarkers) 	

Abbreviations: AA = Anaplastic astrocytoma; ADA = Anti-drug antibody; AE = Adverse event; CTCAE = Common terminology criteria for adverse events; DCR=Disease Control Rate; DOR = Duration of response; GBM = Gliobastoma multiforme; iRECIST = Response evaluation criteria in solid tumors for trials testing immunotherapeutics; iRANO = Immune response assessment in neuro-oncology; ORR = Objective response rate; OS = Overall survival; PFS = Progression free survival; PK = Pharmacokinetics; RANO = Response assessment in neuro-oncology; RECIST 1.1 = Response evaluation criteria in solid tumors 1.1

a) The efficacy endpoints will be based on the local Investigator's assessment. Imaging data on tumor assessment will be collected for a potential retrospective central review of tumor evaluation by blinded readers.

4. Study Design

[figure not shown]
4.1 **Overall Design**

This study is a multi-center, multi-indication, open-label, single-treatment arm, parallel-cohort Phase 2 study of regorafenib in combination with nivolumab in adult participants with selected recurrent or metastatic tumors (HNSCC, ESCC, PDAC, BTC, and GBM/AA) who have been previously treated with one or more systemic therapy for the selected tumor indication. An overview of the study schema is presented in Figure 4–1.

The study will be conducted at approximately 60 sites in North America, Europe and Asia/Pacific. Up to 200 participants who qualify for the study will be treated with regorafenib plus nivolumab.

This study is composed of the following periods: Screening, treatment, active follow-up (FU), and long-term follow up. An overview of the study schema is presented in Figure 4–1.

Figure 4–1 Study Design Overview

[figure not shown]
Abbreviations: C = Cycle; FU = Follow-up; LD = Last dose; Q4W = Every 4 weeks; QD = Daily

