27 JAN 2021

All participants will be assessed for efficacy and safety during Stage 1 and Stage 2. Enrollment may be discontinued for those cohorts that will not pass the pre-defined ORR threshold for Stage 1. In addition, the totality of the data, including the duration and depth of response and overall risk-benefit assessment may be considered in the decision to terminate or continue the expansion after Stage 1.

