5.1 Inclusion Criteria

Participants are eligible to be included in the study only if all the following criteria apply (unless where specified for specific tumor indication). Reintroduction of the same chemotherapy in sequential order and locoregional treatments such as hepatic arterial infusion therapy is not considered as a new line of treatment:

Cohort 1 (HNSCC, IO naïve)

- 101 Cohort 1: Histologically confirmed recurrent or metastatic HNSCC (from any of the following primary sites only: oral cavity, oropharynx, hypopharynx and larynx) that is not amenable to curative intent surgery or chemoradiation.
- 102 Cohort 1: Progressed on or after 1, 2 or 3 lines of prior systemic therapy for recurrent or metastatic disease containing platinum chemotherapy or fluoropyrimidine or cetuximab, or a combination of these agents. Patients should receive standard of care treatment as initial treatment in accordance with local guidelines unless they are intolerant to standard first-line systemic chemotherapy as judged by their treating physician.
 - For Stage 2, participants also qualify if they have recurrent disease within 6 months after the last dose of chemotherapy as part of definitive curative intent therapy (including patients who underwent chemoradiation with or without surgery).
- 103 Cohort 1: Documented HPV/p16 status for oropharyngeal cancer (historical results are acceptable if available).
- 104 Cohort 1: For Stage 2 participants only: Provision of recent tumor tissue defined as tumor tissue obtained within 180 d of enrollment and after the last dose of most recent anti-cancer therapy or tissue from a new biopsy.

Cohort 2 (HNSCC, IO treated)

- 201 Cohort 2: Histologically confirmed recurrent or metastatic HNSCC (from any of the following primary sites only: oral cavity, oropharynx, hypopharynx and larynx) that is not amenable to curative intent surgery or chemoradiation.
- 202 Cohort 2: Progressed on or after 1, 2 or 3 lines of prior systemic therapy for recurrent or metastatic disease containing PD-1/PD-L1 inhibitor alone or in combination with chemotherapy. One of these prior lines should contain a PD-1/PD-L1 inhibitor.

Progression on a prior PD-1/PD-L1 inhibitor regimen should meet the following criteria:

- Has received at least 2 doses of an anti-PD-1/PD-L1 mAb.

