- Has demonstrated disease progression after anti-PD-1/PD-L1 therapy as defined by RECIST. Confirmation of radiographic progression on prior anti-PD-1/PD-L1 therapy is required with a scan confirming progression at least 4 weeks after the initial progression date. Screening scans can be used as the confirmation of progression.
- 203 Cohort 2: Documented HPV/p16 status for oropharyngeal cancer (historical results are acceptable if available).
- 204 Cohort 2: Provision of recent tumor tissue defined as tumor tissue obtained within 180 d of enrollment and after the last dose of most recent anti-cancer therapy or tissue from a new biopsy.

Cohort 3 (ESCC)

- 301 Cohort 3: Histologically or cytologically confirmed recurrent or metastatic ESCC that is not amenable to curative intent surgery or chemoradiation.
- 302 Cohort 3: Progression on or after 1 line of systemic therapy for recurrent or metastatic disease with platinum and/or fluoropyrimidine based regimen.
 - For Stage 2, participants also qualify if they have recurrent disease within 6 months after the last dose of chemotherapy as part of definitive curative intent therapy (including patients who underwent chemoradiation with or without surgery).

Cohort 4 (PDAC)

- 401 Cohort 4: Histologically or cytologically confirmed recurrent or metastatic PDAC that is not amenable to curative intent surgery
- 402 Cohort 4: Progression on or after 1 or 2 lines of systemic therapy for recurrent or metastatic disease with gemcitabine or fluoropyrimidine based regimens

Cohort 5 (BTC)

- 501 Cohort 5: Histologically or cytologically confirmed recurrent or metastatic BTC, namely cholangiocarcinoma (intrahepatic or extrahepatic) or gall bladder cancer, that is not amenable to curative intent surgery, transplantation, or ablative therapies.
- 502 Cohort 5: Progression on or after 1 or 2 lines of systemic therapy for recurrent or metastatic disease containing gemcitabine or fluoropyrimidine or platinum therapy or a combination of these agents

Cohort 6 (GBM/AA)

601 Cohort 6: Histologically or cytologically confirmed Grade IV GBM or Grade III AA (World Health Organization [WHO] criteria) established following either a surgical resection or biopsy. This includes participants with prior diagnosis of lower grade astrocytoma from a biopsy that has been upgraded to a histologically verified glioblastoma or anaplastic astrocytoma after a subsequent definitive surgery. AA is only allowed in Stage 2.

CONFIDENTIAL

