9.5 Interim Analyses

At stage 1, an interim futility analysis for response rate will be conducted per cohort based on patients in the full analysis set (FAS). The evaluation will be based on a clean database of Stage 1 with cut-off date when the last participant of the respective cohort has had the chance to complete 4 cycles of treatment.

At Stage 2, response rates will be analyzed per cohort based on the FAS. Data read out is planned after the last participant of the respective cohort has had the chance to complete 4 cycles of treatment.

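### Should the response rate in the head-and-neck (IO-naïve), oesophageal and glioma cohorts be split because Stage 2 admits participants whom Stage 1 excluded?

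*Protocol*

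**What the plan says.** Three of the six cohorts have wider entry in Stage 2 than in Stage 1.

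- **Cohort 6 (GBM/AA).** Protocol section 4.1 notes that "participants with AA are included only in Stage 2", and inclusion criterion 601 repeats it: "AA is only allowed in Stage 2".
- **Cohort 1 (HNSCC, IO naïve).** Criterion 102 asks for "Progressed on or after 1, 2 or 3 lines of prior systemic therapy for recurrent or metastatic disease containing platinum chemotherapy", fluoropyrimidine or cetuximab. It then adds a second route: "For Stage 2, participants also qualify if they have recurrent disease within 6 months after the last dose of chemotherapy as part of" treatment given with curative intent.
- **Cohort 3 (ESCC).** Criterion 302 asks for "Progression on or after 1 line of systemic therapy for recurrent or metastatic disease with platinum and/or fluoropyrimidine based regimen" and adds the same Stage 2 route.

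Protocol sections 9, 9.1 and 9.2 pool the two stages. The null is 15% and the alternative 30%. A cohort goes on with at least 1 response in 9, adds 21 participants, and is positive at 8 or more of 30. Section 9.4.2 makes the cohort the unit of the primary analysis. Section 9.5 plans a futility look at the Stage 1 response rate in each cohort.

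SAP v3.0 section 5.3.2 shows the response rate by cohort with 80% Clopper-Pearson intervals. Sections 5.3.3 and 5.3.4 plan no sensitivity or supplementary analysis, and section 5.7.2 rules out subgroup analyses.

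**The concern.** The people who decide whether a cohort expands are not quite the people on whom the final answer rests. Stage 1 of the glioma cohort is GBM only. Stage 1 of Cohorts 1 and 3 requires progression on or after treatment for recurrent or metastatic disease. In Stage 2, people can enter who meet neither description, and the protocol states no cap on their number among the 21.

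If they respond at a different rate, the pooled figure describes a mixture. A reader who wants the rate in GBM, or in HNSCC or ESCC already treated for recurrent or metastatic disease, cannot recover it from a by-cohort table. The Stage 1 rate does cover the narrower population, but on about 9 people. At stake is the reading of a positive or negative cohort result, in either direction.

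**Working it through.** **1. The plan's own figures.** Inputs from protocol sections 9, 9.1 and 9.2: continue at 1 or more of 9, add 21, positive at 8 or more of 30, negative at 5 or fewer, 15% versus 30%.

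P(positive | p) = Σ over x = 1 to 9 of P[Bin(9, p) = x] × P[Bin(21, p) ≥ 8 − x]. P(negative | p) adds the Stage 1 stop to the chance of 5 or fewer in total.

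| | Stated | Computed |
|---|---|---|
| P(positive) at 15% | at most 10% | 6.8% |
| P(positive) at 30% | 70% | 70.7% |
| P(negative) at 15% | 70% | 73.0% |
| P(negative) at 30% | 10% | 10.2% |

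The design reproduces. The calculation assumes one common rate for all 30.

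**2. Does mixing break the test?** Let m of the 21 be Stage 2-only entrants with rate q, and let the other 30 − m have rate p, chosen so that the 30-person mean is the null: (30 − m)p + mq = 30 × 0.15 = 4.5. Over m = 1 to 21 and q from 0 to 1, ignoring the Stage 1 stop, the largest P(8 or more of 30) is 7.0%, reached when p = q = 15%. For a cohort whose average rate is 15%, mixing does not raise the false-positive rate above that of a uniform cohort, and it stays under 10%.

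**3. What if a reader wants the Stage 1-type rate instead?** The documents give neither m nor q, so these are scenarios. P(positive) = Σ over x = 1 to 9 of P[Bin(9, p) = x] × P[Bin(21 − m, p) + Bin(m, q) ≥ 8 − x].

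| p | q | m = 0 | m = 3 | m = 7 | m = 10 |
|---|---|---|---|---|---|
| 15% | 10% | 6.8% | 5.8% | 4.6% | 3.8% |
| 15% | 20% | 6.8% | 7.9% | 9.5% | 10.9% |
| 15% | 30% | 6.8% | 10.3% | 16.5% | 22.0% |
| 30% | 15% | 70.7% | 64.8% | 55.7% | 48.3% |

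With three entrants the shift is small. With ten it can be large. These figures describe the pooled rule read as a statement about a subset, and section 9.1 declares no subset hypothesis. They are not error rates of the plan.

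**4. What would a split show?** 80% Clopper-Pearson limits for x of n are the 10th percentile of Beta(x, n − x + 1) and the 90th percentile of Beta(x + 1, n − x). Example counts:

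| Group | Responses | 80% interval | Width (points) |
|---|---|---|---|
| Pooled cohort | 8/30 | 16.2-39.7% | 23.5 |
| Stage 1-type, both stages, 3 entrants | 7/27 | 15.1-39.7% | 25 |
| Stage 1-type, both stages, 7 entrants | 6/23 | 14.3-41.3% | 27 |
| Stage 2-only, 3 entrants | 1/3 | 3.5-80.4% | 77 |
| Stage 2-only, 7 entrants | 2/7 | 7.9-59.6% | 52 |
| Stage 1 alone | 1/9 | 1.2-36.8% | 36 |
| Stage 1 alone | 2/9 | 6.1-49.0% | 43 |

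In these examples the Stage 1-type interval nearly repeats the pooled one, and the Stage 2-only interval is too wide to show a difference.

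**5. Do the added participants fall outside the declared population?** Section 4.1 describes participants "who have been previously treated with one or more systemic therapy for the selected tumor indication". Chemotherapy given with curative intent fits that. AA participants must also meet criterion 602, a first progression after surgery, radiotherapy and temozolomide. The plan accepts similar breadth elsewhere: Cohort 1 pools one to three prior lines, and BTC pools cholangiocarcinoma with gallbladder cancer.

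**The case for a change.** The case for a split is reasonable. The sponsor kept these groups out of Stage 1. Protocol section 2.2 reports about 36% response to first-line systemic therapy in HNSCC and 13 to 18% with a PD-1 inhibitor in second line, so line of treatment may matter, although those figures come from different treatments. The clinical evidence cited for the glioma cohort is in recurrent GBM, and no response rate for AA is given. The addendum also omits baseline characteristics, so it would not show even how many such participants there were. An estimate in Stage 1-type participants from both stages is far tighter than the Stage 1 rate alone (25 to 27 points wide against 36 to 43). The table would cost little: section 8.2.7 collects histology and prior cancer therapies.

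What stands is that such a table would help some readers, most clearly for GBM against AA. What does not follow is that the plan is deficient without it. SAP v3.0 is a deliberately reduced plan for the final report addendum. It refers to SAP v2.0 for design, hypotheses, sample size and the response definition, and to a separate document for table, figure and listing specifications. Neither was available, so the absence of a split is shown only for the addendum's text. For Cohorts 1 and 3 the split would also need treatment intent and last-dose date, which the protocol does not list as collected items. It would be added after the January 2023 primary-completion plan, in an open-label trial.

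**Conclusion.** No change is needed. The eligibility difference is real, but the pooled cohort is the declared target, the test is valid for it (6.8% false positives against a ceiling of 10%), and the 8-of-30 rule is untouched by how results are later displayed. Followed as written, the plan gives a sound answer to its own per-cohort question.

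The remaining limit is one of interpretation. It applies only to a cohort that expanded and enrolled participants who qualify solely by the Stage 2 route. That they have no earlier line for recurrent or metastatic disease is an inference from criteria 102 and 302. Section 4.1 says "Enrollment may be discontinued for those cohorts that will not pass the pre-defined ORR threshold for Stage 1", and the documents do not say whether Cohorts 1, 3 or 6 went on, how many participants used the new routes, or how they responded. If none did, the point is empty; if few did, the scenario shift is small.

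A descriptive split would change no decision and, in the examples worked here, would seldom show whether the groups differ. An author who wishes to report the number of such participants, and the response rate among those meeting the Stage 1 criteria, may do so without a test. That is an optional reporting addition.
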